### **12.3. Investigator's Responsibilities**

Investigator responsibilities are set out in the ICH Guideline for GCP and in the local regulations. Each Investigator participating in this study is required to maintain complete and accurate study documentation in compliance with current GCP standards and all applicable local regulations related to the conduct of a clinical study.

The Principal Investigator will ensure that all persons assisting with the study are adequately informed about the protocol, any amendments to the protocol, the study drug, and their study-related duties and functions. The Principal Investigator will maintain a list of sub-Investigators and other appropriately qualified persons to whom he or she has delegated significant study-related duties.

The Investigator is responsible for keeping a record of all patients who sign an informed consent document and are screened for entry into the study. Patients who fail eligibility requirements must have the reason(s) recorded in the patient's source documents.

The Sponsor, or designee, should inform the EC of any event likely to affect the safety of patients or the continued conduct of the study, in particular any change in safety. Additionally, all updates to the Investigator's Brochure will be sent to the EC. A progress report will be sent to the EC and the protocol will be reviewed annually (e.g., re-approved) or more frequently, as required by the EC or local regulations.

The Investigator will maintain a copy of all correspondence with the EC, including copies of approved documents submitted by the Sponsor or designee. The Investigator will also maintain a copy of the EC membership list with occupation and qualification (or a statement confirming compliance with GCP requirements for committee composition).

The Sponsor or designee is responsible for notifying the EC/RA of the conclusion of the clinical study within 90 days of completion of the study, per the EU Directive. In cases where a study is

terminated early, notification must be made within 15 days of the early termination. The final study report must be submitted within 1 year after study completion.

The Investigator, or a designated member of the Investigator's staff, must be available during monitoring visits to review data, resolve queries and allow direct access to patient records (e.g., medical records, office charts, hospital charts, and study-related charts) for source data verification. The Investigator must ensure timely and accurate completion of eCRFs and queries.

## **12.4. Protocol Amendments**

Any permanent change to the protocol, whether it is an overall change or a change for specific study center(s), must be handled as a protocol amendment. All amendments to the protocol will be written by the Sponsor. The Investigator will not make any changes to this protocol without prior written consent from the Sponsor and subsequent approval by the EC. Except for administrative amendments, Investigators must await EC approval of protocol amendments before implementing the change(s). The Sponsor will ensure submission of any protocol amendments to the appropriate regulatory agencies and EC.

Trial conduct may be impacted in light of the COVID-19 pandemic. Challenges may arise (e.g., quarantines, site closures, travel limitations, interruptions to the supply chain for the investigational product, etc.) leading to difficulties in meeting protocol-specified procedures, including administering or using the investigational product or adhering to protocol-mandated visits and laboratory/diagnostic testing. Taking into consideration recent Regulatory Agency guidance, amendments to protocol defined criteria may be implemented without EC approval or before filing an amendment to the IND/CTA in order to minimize or eliminate immediate hazards or to protect the life and well-being of research participants (e.g., to limit exposure to COVID-19).

Administrative amendments are defined as having no effect on the safety of the research subjects, scope of the investigation, or quality of the study. However, a protocol change intended to eliminate an apparent immediate hazard to patients should be implemented immediately, and the EC notified within 5 days or per local regulations.

When, in the judgement of the chairman of the local EC, the Investigators, and/or the Sponsor, the amendment to the protocol substantially alters the study design and/or increases the potential risk to the patient, the currently approved written ICF will require similar modification. In such cases, repeat informed consent will be obtained from patients enrolled in the study before continued participation under the new amendment.

## **12.5. Audits and Inspections**

The Sponsor's Quality Assurance Unit (or representative) may conduct audits at the study site(s) or remotely. Audits will include, but are not limited to: drug supply, presence of required documents, the informed consent process, laboratory specimen processing, and comparison of eCRFs with source documents. The Investigator agrees to cooperate with audits conducted at a reasonable time and in a reasonable manner.

Regulatory authorities worldwide may also inspect the Investigator during or after the study. The Investigator should contact the Sponsor immediately if this occurs, and must fully and reasonably cooperate with Regulatory inspections.

The Investigator is required to make all study documentation promptly available for inspection, review or audit upon request by Sponsor, its representatives, or any appropriate regulatory agencies.

## **12.6. Quality Control and Quality Assurance**

All aspects of the study will be carefully monitored by the Sponsor or its authorized representative for compliance with applicable government regulations with respect to current GCP and standard operating procedures.

A quality control and quality assurance plan addressing aspects of the study that may impact data integrity or the protection of human subjects may be instituted for this study. Audit findings and follow-up will be documented as appropriate based on Sponsor Standard Operating Procedures.

In light of the COVID-19 pandemic, risk-based approaches to patient safety will be instituted, as applicable and per local regulations. Compliance with Good Clinical Practice (GCP) will be maintained and risks to patient safety and data integrity will be maintained.

## **13. DATA HANDLING AND RECORDKEEPING**

### **13.1. Confidentiality**

All information disclosed or provided by the Sponsor (or designee), or generated or produced during the study including, but not limited to, the protocol, the eCRFs, the Investigator's Brochure, and the results obtained during the course of the study, are confidential. The Investigator or any person under his/her authority agrees to keep confidential and not to disclose the information to any third party without the prior written approval of the Sponsor.

Submission of this protocol and any other necessary documentation to the EC is expressly permitted, EC members having the same obligation of confidentiality. Authorized regulatory officials and Sponsor personnel (or designee) will be allowed full access to inspect and copy the records. The copied and inspected records will remain at the site and will not be transmitted or removed from the site. Study drug, patient bodily fluids, and/or other materials collected shall be used solely in accordance with this protocol, unless otherwise agreed to in writing by the Sponsor and responsible ethics committee(s) or regulatory authorities.

Patients' names may, however, be made known to a regulatory agency or other authorized officials in the event of inspections. Documents containing the full name or other personally identifiable information of the patient are to remain at the site. This information will not be transferred to the Sponsor nor be contained in regulatory filings.

### **13.2. Patient Data Protection**

Prior to any testing under this protocol, candidates must provide all authorizations required by local law (e.g., protected health information authorization).

Patients will be identified only by unique patient numbers in eCRFs and other datasets generated for this study. The patient will not be identified by name in the eCRF, in any study samples or study reports. All data generated in this study is for research purposes only. The Sponsor, its partner(s) and designee(s), and various government health agencies may inspect the records of this study. Every effort will be made to keep the patient's personal medical data confidential.

The Sponsor will protect individual patient information to the fullest extent possible during this study. At no time will a patient become identified in any publication or presentation. However, the patient may have to become identified in the event of a regulatory authority audit or inspection in order to verify the accuracy of the data. Access to patient information is at the discretion of the Sponsor and cannot occur prior to database lock or other specified events as determined solely by the discretion of the Sponsor.

### **13.3. Data Collection**

All data obtained for analysis in the clinical study described in this protocol will use an electronic data capture system. Data reported in the eCRFs should be consistent with and substantiated by the patient's medical record and original source documents. Any discrepancies must be explained.

Prior to the start of the study, the Principal Investigator will complete a Delegation of Authority form (Site Signature and Delegation Log), showing the signatures and handwritten initials of all individuals and the delegation of responsibilities, such as identifying those individuals who are authorized to make or change entries on eCRFs.

### **13.4. Case Report Form Completion**

Data within the eCRF will be monitored by a Clinical Research Associate according to the Monitoring Plan. Queries will be generated based on discrepancies found while monitoring. Site personnel will review and respond to these queries appropriately. Additionally, the Sponsor's designee and the Sponsor may periodically perform aggregate data reviews, which could result in queries being generated for site personnel resolution. The completed eCRF for each patient must be signed and dated by the Principal Investigator to signify that the Principal Investigator has reviewed the eCRF and certifies it to be complete and accurate.

### **13.5. Database Management, Data Clarification, and Quality Assurance**

The Sponsor's designee (i.e., a designated Contract Research Organization) will be responsible for data management. Data Management will develop a Data Management Plan (DMP) document, and provide it to the Sponsor for approval. The DMP document will define all activities in the data collection and cleaning process. The detailed DMP will be based on the protocol, work scope, contract, analysis plans, data-flows, eCRFs, data cleaning procedures, other supporting documents, and data management standards and practices.

The programmed data validations will be run to check for database completeness and consistency, and queries will be generated upon data entry or via review by a Clinical Data Manager after entry. The sites will respond to the data queries in a timely manner.

Quality control procedures will be conducted prior to database lock according to the designated Contract Research Organization standard operating procedures.

When the database has been declared to be complete and accurate, it will be locked. Any changes to the database after that time will only be made by joint written agreement between the Sponsor, Statistician, Data Manager, and Quality Assurance Auditor according to designated standard operating procedures of the Contract Research Organization.

### **13.6. Inspection of Records**

According to the ICH guidelines for GCP, the Sponsor or designee must verify data entered in the eCRF entries against the source documents. The objective of source document verification is to comply with GCP and international regulatory requirements and to reduce the risks of fraud. Source document verification means ensuring that source documents are an accurate and confirmable reflection of the patient's evaluations during participation in the study and that all relevant information recorded in the source document is accurately entered into the eCRF. All source documents should be correctly labeled and filed and associated with a single, verifiable patient.

All data required for this study should be captured in source notes. No data obtained by the Investigator or other study personnel should be captured directly in the eCRF. All source documents pertaining to this study will be maintained by the Investigator and made available for inspection by authorized persons. If electronic progress notes and other electronic source documents are not compliant with applicable regulatory guidance, they are not considered a valid source for this study. All patient progress notes must be dated and signed at the time of the visit. The Sponsor reserves the right to terminate the study for refusal of the Investigator to supply original source documentation for this clinical study.

The Investigator will note in a source independent from the eCRF the following information:

- Information to confirm that the patient exists, as applicable per local regulations (e.g., initials, year of birth, and sex);
- Confirmation that the patient satisfies the inclusion/exclusion criteria;
- Confirmation that the patient is taking part in the clinical study;
- Confirmation of the informed consent process;
- Visit dates and documentation of protocol assessments and procedures;
- Information concerning all adverse events;
- Details of concomitant and investigational medications.

Source document verification is not a substitute for clinical study monitoring, the purpose of which is to ensure that the protocol has been followed correctly, the eCRF has been fully and accurately completed, source document verification has been carried out, and the study timelines and enrollment goals and requirements have been met. In light of the COVID-19 pandemic, source document verification may occur remotely, as applicable, and in accordance with local regulations. Additional detail on remote source document verification will be provided in the study plans.

### **13.7. Retention of Records**

For all trials in which the clinical trial data are used to support a marketing authorization, per Directive 2003/63/EC (amending Directive 2001/83/EC), study records will be retained for at least 15 years after completion or discontinuation of the trial or at least two years after the granting of the last marketing authorization in the European Union (when there are no pending or contemplated marketing applications in the EU) or for at least two years after formal discontinuation of clinical development of the investigational product, whatever is the longest.

The Investigator must maintain all study documentation as confidential, and take measures to prevent accidental or premature destruction of these documents.

The Investigator must notify the Sponsor prior to destroying any study essential documents.

If the Investigator can no longer ensure archiving, they shall inform the Sponsor. The relevant records shall be transferred to a mutually agreed upon designee.

## **14. PUBLICATION POLICY**

[figure not shown]
[figure not shown]
The results of this study may be published in a medical publication, journal, or may be presented at a medical conference or used for teaching purposes. Additionally, this study and its results may be submitted for inclusion in all appropriate health authority study registries, as well as publication on health authority study registry websites, as required by local health authority regulations. Selection of first authorship will be based on several considerations, including, but not limited to study participation, contribution to the protocol development, and analysis and input into the manuscript, related abstracts, and presentations in a study.

## 16. APPENDICES

### 16.1. Severity of Alopecia Tool (SALT)

Olsen/Canfield

|  |  |                               |  |
|--|--|-------------------------------|--|
| Left Quadrant Raw Score (LRS)  |  | Top Quadrant Raw Score (TRS)  |  |
| Right Quadrant Raw Score (RRS)   |  | Back Quadrant Raw Score (BRS) |  |
| Total SALT Score $[(LRS \times 0.18) + (RRS \times 0.18) + (TRS \times 0.40) + (BRS \times 0.24)]$ |  |                               |  |

1. LIST OF ABBREVIATIONS

Table 1: List of Abbreviations

Abbreviation	Term
AE	Adverse event
ALT	Alanine aminotransferase
ATC	Anatomical-Therapeutic-Chemical
BID	Twice daily dosing
BMI	Body mass index
COVID-19	Coronavirus disease of 2019
CPK	Creatine phosphokinase
CSR	Clinical study report
CTCAE	Common terminology criteria for adverse events
ECG	Electrocardiogram
eCRF	Electronic case report form
e.g.	Exempli gratia
i.e.	Id est
IQR	Interquartile Range
IWRS	Interactive web response system
MedDRA	Medical Dictionary for Regulatory Activities
OLE	Open-label extension
PCS	Potentially clinically significant
PML	Progressive multifocal leukoencephalopathy
QTcF	QT interval corrected for heart rate (Fridericia's method)
SALT	Severity of Alopecia Tool
SAP	Statistical analysis plan
SARS-CoV-2	Severe acute respiratory syndrome coronavirus 2
SD	Standard deviation
TB	Tuberculosis
TEAE	Treatment-emergent adverse events
WHO	World Health Organization

2. PURPOSE OF THE ANALYSES

This statistical analysis plan (SAP) provides a detailed description of the strategy and statistical methodology to be used for analysis of data from the CP543.5002 current protocol version.

The purpose of the SAP is to describe the pre-specified statistical approaches to the analysis of study data prior to database lock. This analysis plan is meant to supplement the study protocol. If differences occur between analyses described in the SAP and the current protocol, those found in this SAP will assume primacy. Any deviations from this plan will be described in the Clinical Study Report (CSR).

3. PROTOCOL SUMMARY

The overall objectives of the study are to evaluate long-term safety of CTP-543 and to assess long-term effects of CTP-543 on treating hair loss in adult subjects with moderate to severe alopecia areata.

Subjects with alopecia areata who previously participated in a qualifying Phase 3 clinical trial (study CP543.3001 or study CP543.3002) with CTP-543 and who complete the 24-week Treatment Period on Study Medication (active or placebo), have the opportunity to enroll in this open-label extension (OLE) study in which they will receive daily treatment with CTP-543. Only subjects in the European Union will be included in this OLE study. At the Week 52 visit, patients will be assessed for treatment success (Responders) defined as patients having an absolute SALT score of ≤ 20 at Week 52. These Responders will be eligible to continue in the OLE extension for up to a maximum of an additional 52 weeks. Non-responders will complete the study at Week 52.

Safety will be evaluated by clinical laboratory measurements, adverse events (AEs) and physical exams. SARS-CoV-2 testing will be performed at all visits. Severity of Alopecia Tool (SALT) assessments will be performed periodically for efficacy, as described in the Schedule of Events Tables in Section 14.1.

Subjects will provide written informed consent prior to completing any eligibility procedures for the OLE study. Following the Day 1 visit, eligible subjects were enrolled and study drug was dispensed. Initially, subjects were assigned to receive daily treatment with CTP-543 at a dose of 8 mg BID or 12 mg BID according to the following criteria:

Previous Treatment in Qualifying Trial	Treatment Assignment in OLE
Placebo BID	8 mg BID or 12 mg BID
8 mg BID	8 mg BID
12 mg BID	12 mg BID

Placebo subjects were randomized via the study Interactive Web Response System (IWRS) in a 1:1 ratio to 8 mg BID or 12 mg BID. The randomization schedule was generated prior to subject enrollment from studies CP543.3001 and CP543.3002.

Following reports of thrombosis with 12 mg BID after long-term administration of CTP-543 and discussions with the US Food and Drug Administration (FDA), the 12 mg BID dose was immediately discontinued and communicated under an Urgent Safety Measure. Due to implementation of this urgent safety measure, all patients previously assigned to the 12 mg BID dose will be dose reduced to the 8 mg BID dose, should they elect to continue in the trial, for the duration of the trial up to a total of 52 weeks for non-responders or a maximum of 108 weeks for responders.

At the Week 52 visit, subjects will be assessed for treatment success (Responders) defined as subjects having an absolute SALT score of ≤ 20 . These Responders will continue in the OLE extension for an additional 52 weeks. Non-responders will complete the study at Week 52. Additionally, subjects should be withdrawn from the study if in the Investigator's opinion

Sun Pharmaceutical Industries, Inc.
Statistical Analysis Plan – CP543.5002

continued study participation is undesirable or the risk-benefit profile has become unfavorable. Additional withdrawal criteria can be found in Section 7.3 of the protocol.

Subject safety will be monitored throughout the study. During the first 12 weeks, hematology, serum chemistry, and lipids will be conducted under fasted conditions every 4 weeks. Following 12 weeks on treatment, subjects will return to the clinic every 8 weeks for safety assessments until the completion of the study or until withdrawal from the study. At each study visit, an assessment should also be undertaken for any changes in the physical exam, or symptoms such as pain, swelling or tenderness in leg(s), persistent breathing difficulties or shortness of breath, or severe headache, that are suggestive of an increased risk of thromboembolism. Patients must be withdrawn if they have a prior history of thrombotic event(s) or experience a thromboembolic event.

Serum pregnancy testing will be performed at all in-clinic visits. To minimize subject burden of additional clinic visits, urine pregnancy testing will be performed by the subject at home on Weeks 16, 24, 32, 40, 48 and 4-weeks post the final study visit. For responders, additional home pregnancy testing will be performed at Weeks 56, 64, 72, 80, 88, 96, 104 and 4-weeks post the final study visit. The test date and result will be documented in a subject diary and brought to each in-clinic study visit by the subject. Significant cytopenias or other hematologic abnormalities will be managed by severity through dose interruption, or discontinuation, and signs and symptoms of infection will be closely monitored and treated promptly. Less significant changes in laboratory values may warrant clinical intervention and the Investigator should use his/her best clinical judgement when considering a dose interruption, whether for singular or aggregate laboratory results outside of the normal range, or for other clinical signs, symptoms, or considerations that suggest dose interruption is in the best interest of the subject. Subjects who experience intolerable symptoms during treatment may discontinue the study at any time. Subjects may withdraw consent at any time.

Assessment of treatment response with SALT for efficacy will occur every 4 weeks for the first 12 weeks, then every 8 weeks thereafter until study completion.

4. GENERAL ANALYSIS AND REPORTING CONVENTIONS

The following is a list of general analysis and reporting conventions to be applied to this study, unless otherwise specified. Departures from these general policies will be described, if applicable, in the appropriate sections of this SAP. When this situation occurs, the rules set forth in the specific section take precedence over the general policies.

All data displays (tables, listings, and figures) will have a header showing the sponsor company name, protocol number, and page number, as well as a footer indicating file name, run date/time, and display status (i.e. “DRAFT” or “FINAL”). Unless otherwise noted, summary tables and data listings will be summarized by treatment group CTP-543 8 mg BID, CTP-543 12 mg BID, and Total CTP-543. All data for analysis will be listed by-subject and by CTP-543 8 mg or 12 mg BID.

Categorical variables will be summarized using counts (n) and percentages (%) and will be presented in the form “n (xx.x)”, with percentages rounded to one decimal place. If a count is 0, no percentage will be shown. If a percentage is 100%, 100.0 will be shown. To ensure completeness, summaries for categorical variables will include all categories, even if no subjects had a response in a particular category. Unless otherwise specified, the denominator for each percentage will be based on the number of subjects in the population being summarized (i.e. header N).

Continuous variables will be summarized using mean, standard deviation (SD), minimum, maximum, median, and number of subjects. The mean and median will be reported to an additional level of precision than the original observations, and the standard deviation will be reported to two additional levels of precision than the original observations. The minimum and maximum will be the same precision as the original collected data. The precision for some original collected data and derived variables are longer than required for clinical interpretation (e.g., >15 decimals). In these situations, the number of decimal places will be determined by the table of precision that will be included with the table shells.

Summary tables and data listings:

- No preliminary rounding will be performed; rounding will only occur after analysis.
- Data from each subject will be separated by a blank line. Within a data listing, if a descriptive item appears line after line, only the first occurrence will be displayed (e.g., in Listing of Vital Signs, subject number, date and visit will only be displayed on first row when presenting all parameters collected at same visit). Repetition of actual results or outcomes (e.g., AEs, lab results, vital sign values) will not be collapsed.
- Data listings will be sorted by CTP-543 dose, subject, and date and/or time of assessment, as applicable, unless otherwise specified.
- Whenever change from baseline or change to baseline is calculated, baseline will be defined and presented in two different ways, with a “pre-zero baseline” and a “CP543.5002 study baseline” as described in Section 6.2. Assessments for physical exams, clinical laboratory tests, 12-lead electrocardiograms (ECG), and SALT will be carried over from the preceding clinical trial database into this study database and be used as the subject’s baseline assessment.

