#### **8.4.1. Continued Eligibility Beyond Initial 52-Weeks of Treatment**

At the Week 52 visit, patients will be assessed for treatment response, defined as achieving a SALT score of  $\leq 20$  to determine their eligibility to continue treatment. Patients who meet responder criteria (SALT score of  $\leq 20$ ) will be eligible to continue to receive CTP-543 for an additional year. Patients who do not meet the defined criteria of SALT  $\leq 20$  will be deemed a non-responder and will complete the study at the Week 52 visit per the Schedule of Events (Table 1 and Table 2).

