5. ANALYSIS SAMPLES

The All Enrolled Population will be defined as all subjects who signed informed consent.

The Safety Population will be defined as all subjects who received at least 1 dose of CTP-543 in this study.

The Efficacy Population will be defined as all subjects who received at least 1 dose of CTP-543 in this study and have at least 1 post-baseline SALT assessment in this study.

Subjects will be analyzed under treatment groups as specified in Section 4.1.

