9. SAFETY EVALUATION

9.1. Overview of Safety Analysis Methods

All safety summaries will be descriptive with no statistical hypothesis testing and based on the Safety Population. Safety assessments will be summarized by treatment group and overall, as specified in Section 4. All safety endpoints will be listed in by-subject data listings.

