9.5. Clinical Laboratory Evaluation

Clinical laboratory samples should be collected at the beginning of each clinic visit and just prior to a dose on all Study Visit Days and will be processed by a central laboratory. In the event a subject is unable to attend an in-clinic visit due to COVID-19, clinical laboratory blood draws may be performed by a Home Health Care agency or a local laboratory.

Clinical laboratory variables will be presented in 3 ways. First, the mean change from baseline to each scheduled assessment will be summarized descriptively by dosing regimen for each

Sun Pharmaceutical Industries, Inc.
Statistical Analysis Plan – CP543.5002

clinical laboratory variable specified in this protocol. Change from baseline will be summarized separately for the “pre-zero” baseline and the CP543.5002 study baseline (see Section 6.2). Values will only be included if the subject had both a baseline and post-baseline value for that parameter.

Second, treatment-emergent potentially clinically significant (PCS) laboratory values will be identified. Potentially clinically significant values are defined as those that meet Grade 3 or Grade 4 toxicity criteria from the common terminology criteria for adverse events (CTCAE) criteria (or Grade 2 or higher for platelets). Laboratory values will be graded using CTCAE version 5.0, for those values included. CTCAE grades will be based solely on numeric results and without regard to other symptoms based on clinical judgment. For laboratory parameters whose CTCAE grading is independent of baseline criteria, treatment-emergent PCS laboratory values are those in which the CP543.5002 study baseline value is not PCS and the post-baseline value is PCS. For laboratory parameters whose CTCAE grading is dependent upon baseline criteria, any post-baseline grading of Grade 3 or Grade 4 (or 2 or higher in the case of platelets) will be considered treatment-emergent, and values will only be included if the subject had both a baseline and post-baseline value for that parameter. The number and percentage of subjects with treatment-emergent PCS laboratory values will be summarized by treatment group and overall for each clinical laboratory variable, separately for the “pre-dose” baseline and the CP543.5002 study baseline. Results will be presented by post-baseline visit and overall; for this analysis, the visit with the highest CTCAE grade value within an analysis window will be selected.

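### By-visit percentages of treatment-emergent PCS laboratory values default to header N, so Weeks 60-108 are understated once Week 52 non-responders have left

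*SAP*

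**What the plan says.** SAP Section 4 gives the general rule: "Unless otherwise specified, the denominator for each percentage will be based on the number of subjects in the population being summarized (i.e. header N". It allows exceptions, in which case "the rules set forth in the specific section take precedence over the general policies".

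For safety outputs, SAP Section 9.1 states: "All safety summaries will be descriptive with no statistical hypothesis testing and based on the Safety Population". SAP Section 5 defines that set: "The Safety Population will be defined as all subjects who received at least 1 dose of CTP-543 in this study". Later attendance plays no part in membership.

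For the laboratory table, SAP Section 9.5 states: "The number and percentage of subjects with treatment-emergent PCS laboratory values will be summarized by treatment group and overall for each clinical laboratory variable". It adds: "Results will be presented by post-baseline visit and overall". It gives no denominator for the visit rows. The safety windows in SAP Section 4.2 (Table 2) run through Week 108.

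Under Protocol Section 8.4.1, a patient who does not reach SALT 20 or below at Week 52 "will be deemed a non-responder and will complete the study at the Week 52 visit". SAP Section 3 repeats this.

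SAP Section 12 cites a sentence from Protocol Section 11.2.3.2 that covers two summaries, investigator-judged abnormal values and treatment-emergent PCS values. It then says that the analysis is removed because of the CRF design.

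**The concern.** After Week 52 the numerator and denominator describe different groups. Only responders who continue can have a laboratory value at Week 60 or later, but the default denominator still holds every dosed subject in the column. Someone who left at Week 52 contributes to the percentage exactly as if tested and found free of a PCS value.

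Long-term safety is a stated objective, and these percentages are among its outputs. If the risk among those tested were constant, the displayed rate would still drop between Week 52 and Week 60 because of the protocol-mandated exit alone. A reader could take that drop for fewer abnormalities with longer exposure. The percentage format in SAP Section 4 gives a count and a percentage but not the number tested.

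**Working it through.** **Step 1. Does any rule override header N?** SAP 9.5 has an inclusion condition, worded as follows for the change-from-baseline summary: "Values will only be included if the subject had both a baseline and post-baseline value for that parameter". The PCS paragraph repeats the condition only for parameters whose CTCAE grading depends on baseline. It asks for some post-baseline value, not a value at the visit in question. A patient who left at Week 52 with earlier tests on file meets it. No other text in SAP 9.5 sets a denominator, so the Section 4 default applies.

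**Step 2. Formula.** The documents state no sample size, Week 52 responder share, dropout rate or PCS rate, so there is no plan figure to reproduce. Let r be the share of a column that continues past Week 52, d the later loss among those who continue, and p the rate among those assessed at the visit.

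- Displayed percentage = p × r × (1 − d)
- Understatement factor = p / displayed = 1 / [r × (1 − d)]

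**Step 3. Range over assumed r.** The last two columns use p = 5%, d = 0 and an assumed header N of 300, all for illustration.

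| r (assumed) | Factor, d = 0 | Factor, d = 20% | Subjects assessed | Displayed when p = 5% |
|---|---|---|---|---|
| 0.30 | 3.33 | 4.17 | 90 | 4.5/300 = 1.5% |
| 0.40 | 2.50 | 3.12 | 120 | 6/300 = 2.0% |
| 0.50 | 2.00 | 2.50 | 150 | 7.5/300 = 2.5% |
| 0.60 | 1.67 | 2.08 | 180 | 9/300 = 3.0% |
| 0.70 | 1.43 | 1.79 | 210 | 10.5/300 = 3.5% |
| 0.80 | 1.25 | 1.56 | 240 | 12/300 = 4.0% |

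With the number assessed as denominator, every row shows 5.0% and the factor is 1.0.

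**Step 4. The only related figures in the documents.** Protocol Section 4.2 gives the share with SALT 20 or below at Week 24 of the parent trials. Used as a stand-in for r with d = 0:

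- CP543.3001: 8 mg BID, 1/0.296 = 3.38; 12 mg BID, 1/0.415 = 2.41
- CP543.3002: 8 mg BID, 1/0.330 = 3.03; 12 mg BID, 1/0.383 = 2.61

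This is a weak proxy. Continuation is decided after a further 52 weeks on active drug, and former placebo patients (0.8% at Week 24) have by then also been treated for 52 weeks.

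**Step 5. Which rows are affected.** The overall row counts a subject with a PCS value at any post-baseline visit, so it lacks this visit-level mismatch. Visits up to Week 52 shrink only by the share already withdrawn.

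**The case against.** The strongest objection is that the table shells, which are attached to the SAP but not in the public file, may set a by-visit denominator. That is possible. However, SAP Section 4 promises that departures will be described in the relevant SAP section, and 9.5 describes none. Where the SAP wants a different denominator, as for the discontinuation reasons in Section 6.1, it says so. What stands is a limit on the claim: it concerns the visible SAP text, not tables already produced.

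Second, SAP Section 12 can be read as removing the PCS table. The reason given there, CRF design, fits the investigator-judged summary. It does not fit PCS grades, which 9.5 bases on numeric results alone, and 9.5 still plans the table in detail. The two sections need to be reconciled.

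Third, everything is descriptive, and other outputs show the attrition: disposition, exposure categories up to 108 weeks, and the subject counts in the continuous laboratory summaries by visit. A careful reader could recover an approximate denominator. This lowers the stakes but does not correct the percentage.

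Two stronger readings are tempting, and the documents do not support them:

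- **That the understatement is established as two- to three-fold.** This would need 33-50% of the column to be assessed at the visit, a share that neither document states.
- **That the 12 mg BID column tends to zero against a fixed N.** Under SAP Section 4.1, patients with a qualifying reduction are classified in the 12 mg-to-8 mg column, so they leave the 12 mg column's N as well as its numerator. That column's sparsity comes from its definition, and a new denominator would not cure it.

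One factor also cannot serve all columns. The urgent-safety reductions are dated on or after 28 April 2023 (SAP Section 8.2.3.1), and estimated first enrolment was September 2021. Anyone reduced after Week 52 was already a continuing responder, so the 12 mg-to-8 mg column may retain a larger share. The mix is unknown.

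**Conclusion.** The point holds for the by-visit PCS rows at Weeks 60-108. The direction follows from the text: any exit at Week 52 lowers these percentages relative to the rate among those tested. The size is conditional on the unstated fraction still assessed. Over assumed continuation of 30-80% with no later loss, the factor runs from about 3.3 down to 1.25. It is larger with later dropout and can vary by column. It rests on the Section 4 default being applied as written and on the table in 9.5 being produced. No hypothesis test depends on it. It is nonetheless worth correcting, because these percentages bear on a stated objective and the correction needs no new data.

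**What to change.** In SAP Section 9.5, state that the denominator for each by-visit PCS percentage is the number of subjects in that treatment column with a gradable value for that parameter in that visit window, and with a baseline value where grading or emergence requires one. Display it as n/N1. Keep header N for the overall row.

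In SAP Section 12, state that only the investigator-judged summary of clinically significant abnormal values is removed, so that it agrees with 9.5.

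The cost is one sentence in 9.5, a change to the table shell and a clarification in Section 12. Late-visit percentages will be higher and less precise. They will describe continuing responders only, and a table footnote should say so.
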